9.1 Clinical Assessments

9.1.1 Concomitant Medications

All concomitant medication will be documented at screening, at all visits and at early termination when applicable, with any changes in concomitant medication during the study recorded in the eCRF. The dose, route, unit frequency of administration, indication for administration and dates of medication will be captured.

9.1.2 Demographic and Baseline Characteristics

Demographic information (year of birth, ethnicity/race, height, weight, as permitted by local regulations) will be recorded at screening. Weight will also be recorded on the day of each PET scan (Visits 2 and 3) prior to administration of each radiopharmaceutical.

9.1.3 Medical History

Medical history, including concomitant disease record, information regarding underlying chronic diseases and family history of cancer will be recorded at screening. Prostate cancer history (diagnosis and prior therapies) and other clinically significant diagnoses that may affect study assessments (e.g., overactive bladder, urinary stasis), in the judgment of the investigator, will be recorded.

9.1.4 Imaging Studies

All patients will receive the PSMA PET scans in the following order: piflufolastat (^{18}F) (Scan 1; Visit 2) and flutufolastat (^{18}F) (Scan 2; Visit 3). Further details of the imaging acquisition protocol are provided in [Section 11](#).

9.1.5 Physical Examination

Not applicable.

9.1.6 Vital Signs

Not applicable.

9.1.7 PSA Levels

Patients' PSA level will be collected at screening (within 14 days of Visit 2) according to site standard of care laboratory testing.

9.2 Clinical Laboratory Measurements

Not applicable.

10 EVALUATIONS BY VISIT

10.1 Visit 1 – Screening (Days -14 to 1)

1. Review the study with the patient and obtain written informed consent and HIPAA authorization.
2. Assign the patient a unique screening number.
3. Review eligibility criteria and patient suitability for enrollment.
4. Record demographic data, height and weight, medical history (general and prostate cancer history) and concomitant medications.
5. Collect PSA value according to site standard of care laboratory testing (within 14 days of Visit 2).
6. Commence AE monitoring.
7. Schedule patient for Visit 2 within 14 days of consent.

10.2 Visit 2 – Scan 1 (Day 1)

1. Record any changes to concomitant medications and any AEs since screening (Visit 1).
2. Record pre-piylufolastat (^{18}F) administration weight.
3. Administer piylufolastat (^{18}F) and perform PET scan. Results of the image interpretation by the local site reader should be recorded in the eCRF.
4. Schedule patient for Visit 3, which should be at least 24 hours after the piylufolastat (^{18}F) PET scan, but within 10 calendar days.

Note: Visit 1 (screening) and Visit 2 (Scan 1) may be combined if the investigator decides to screen a patient and perform the piylufolastat (^{18}F) PET scan on the same day. In such cases:

- All assessments listed in [Section 10.1](#) (Visit 1 [screening]) should be performed prior to the piylufolastat (^{18}F) injection and PET scan;
- The investigator should ensure ample time is made available for the patient to think about the study and ask questions before agreeing to participate (see [Section 17.3](#) for details of informed consent requirements).

10.3 Visit 3 – Scan 2 (Days 2 to 10)

Note: this visit should occur at least 24 hours later than, but within 10 calendar days of Scan 1.

1. Record any changes to concomitant medications and any AEs since Visit 2 (Day 1).
2. Record pre-flotufolastat (^{18}F) administration weight.
3. Administer flotufolastat (^{18}F) and perform PET scan. Results of the image interpretation by the local site reader should be recorded in the eCRF.
4. Schedule patient for a telephone call (Visit 4) on the day after the scan.

10.4 Visit 4 – 24 Hours After Scan 2 (Days 3 to 11; Telephone)

1. Perform post-flotufolastat (^{18}F) scan safety monitoring telephone call, including recording any AEs and changes to concomitant medications since Visit 3.

11 IMAGING PROTOCOL

A summary of the imaging protocol for piflufolastat (^{18}F) (Scan 1 [Visit 2]; as part of routine clinical care) and flutufolastat (^{18}F) (Scan 2 [Visit 3]) is provided below in [Sections 11.1 to 11.5](#). Full details are in the Study Imaging Manual (aka Technical Operations Manual).

11.1 PET Scanner

A dedicated hybrid PET/CT is mandatory. The selected scanner must be approved by the imaging core laboratory (Invicro, LLC). For each patient, the same PET/CT scanner must be used for both the piflufolastat (^{18}F) PET scan (Scan 1 [Visit 2]) and the flutufolastat (^{18}F) PET scan (Scan 2 [Visit 3]). Full details are in the Study Imaging Manual (aka Technical Operations Manual).

11.2 Injection Administration

See [Section 8.9](#) for a summary of the administration instructions for each radiopharmaceutical. Both radiopharmaceuticals will be administered as single doses according to their respective approved USPIs.

See Section 2.2 of the [PYLARIFY USPI](#) and [POSLUMA USPI](#) for further details.

11.3 PET/CT Acquisition

The piflufolastat (^{18}F) PET scan (Scan 1) will be performed on Day 1 (Visit 2) per standard institutional practice and in line with the [PYLARIFY USPI](#). For each patient, the flutufolastat (^{18}F) scan acquisition technical parameters should be equivalent to the piflufolastat (^{18}F) PET scan acquisition protocol for that particular site.

- Concurrent use of diuretics (e.g., Lasix [furosemide]) or urinary catheterization (for the purpose of improving PET images) are not permitted for either PSMA PET scan (see [Section 7.2](#)).
- Patients should not have an x-ray contrast agent or any other PET radiotracer within 24 hours prior to either PSMA PET scan (see [Section 7.2](#)).
- Patients should void immediately prior to imaging.
- Position the patient supine with arms above the head.
- For piflufolastat (^{18}F), begin image acquisition 50 to 90 minutes post-injection.
- For flutufolastat (^{18}F), begin image acquisition 50 to 70 minutes post-injection.
- Axial scan length for both scans will be matched to the piflufolastat (^{18}F) scan length at site.
- Scan duration is 12 minutes to 40 minutes depending on the number of bed positions (typically six to eight) and acquisition time per bed position (typically 2 minutes to 5 minutes).
- A minimum time of 24 hours is required between the PSMA PET (i.e., piflufolastat (^{18}F) and flutufolastat (^{18}F)) scan acquisitions.

Full details of the image acquisition protocol are in the Study Imaging Manual (also known as Technical Operations Manual).

Patients should be instructed to drink water prior to administration of each radiopharmaceutical to ensure adequate hydration, and to continue drinking and voiding frequently for the first few hours following administration to reduce radiation exposure.

11.4 Image Transfer

PET scan data requires central assessment and therefore images should be submitted as soon as the scan is complete rather than batched at the end of the study. Following completion of each PET scan at the study site, the scan data will be promptly sent to the imaging core laboratory (Invicro, LLC) using a cloud-based submission portal. The portal includes automatic pseudonymization of the scan. Full details are in the Study Imaging Manual (also known as Technical Operations Manual).

In addition, results of the image interpretation by the local site reader should be recorded in the eCRF (see [Sections 10.2](#) and [10.3](#)).

11.5 Image Analysis

For the primary endpoint analysis, VOIs will be placed over the urinary bladder and radioactivity (SUV metrics) will be assessed following administration of each radiopharmaceutical.

For secondary and tertiary endpoints, both the piflufolastat (^{18}F) and flutufolastat (^{18}F) PET scans will be read by two independent nuclear medicine physicians or nuclear radiologists who are blinded to the patient's clinical history but have been trained to read scans for each respective radiopharmaceutical using product-specific training and in line with the respective FDA-approved USPI for the respective radiopharmaceutical. To facilitate use of the appropriate product-specific training, the independent readers will be unblinded to the administered agent. Any image interpretation disagreements will be resolved by a third independent adjudicator. Full details are in the Study Image Review Charter.

12 ADVERSE EVENT REPORTING AND DOCUMENTATION

12.1 Adverse Events

An AE is any untoward medical occurrence in a clinical investigation of a patient administered a pharmaceutical product and that does not necessarily have a causal relationship with the product. An AE is therefore any unfavorable and unintended sign (including an abnormal laboratory finding, if applicable), symptom or disease temporally associated with the administration of a pharmaceutical product, whether or not related to that product. An unexpected AE is one of a type not identified in nature, severity, or frequency in the USPI, or of greater severity or frequency than expected based on the information in the USPI.

The collection period for all AEs will begin after informed consent is obtained and end after procedures for the final study visit have been completed (i.e., post-procedural safety monitoring telephone call 24 hours after the flutufolastat (^{18}F) PET scan [Visit 4]). AEs will be assigned as treatment-emergent or non-treatment-emergent as outlined in [Table 2](#).

Table 2: Treatment-emergent Adverse Event Definitions

Time Period	Categorization

 AEs occurring after informed consent (Visit 1) but prior to administration of piflufolastat (^{18}F) (Scan 1; Visit 2) 	
 Non-treatment-emergent

 AEs occurring from the time of administration of piflufolastat (^{18}F) (Scan 1; Visit 2) to the time of administration of flutufolastat (^{18}F) (Scan 2; Visit 3) 	
 Treatment-emergent: attributable to piflufolastat (^{18}F) 
Note: any TEAEs attributable to piflufolastat (^{18}F) will not be assigned causality (related/not related to piflufolastat (^{18}F))

 AEs occurring from the time of administration of flutufolastat (^{18}F) (Scan 2; Visit 3) to the final post-flutufolastat (^{18}F) PET safety monitoring telephone call (Visit 4) 	
 Treatment-emergent: attributable to flutufolastat (^{18}F)

Abbreviations: ^{18}F =fluorine-18; AE=adverse event; PET=positron emission tomography.

As the patient will receive a (^{18}F) PET scan irrespective of their participation in this study, AEs will be collected when the patient returns to the site for Scan 2 (Visit 3). No post-piflufolastat (^{18}F) PET safety monitoring telephone call is planned and AEs will not be solicited, but any AEs volunteered by the patient will be reported in the site's source documents and patient's eCRF. **Suspected adverse reactions for piflufolastat (^{18}F) should be reported to the Marketing Authorization Holder (Progenics Pharmaceuticals, Inc) or the FDA as detailed in the [PYLARIFY USPI](#).**

For the IP, flutufolastat (^{18}F), the investigator (or designee) will probe, via discussion with the patient at the post-procedural safety monitoring telephone call 24 hours after the flutufolastat (^{18}F) PET scan (Visit 4), for the occurrence of AEs and record the information in the site's source documents and patient's eCRF.

Adverse events will be described by duration (start and stop dates and times), severity, outcome, and treatment, and for the IP (flutufolastat (^{18}F)), relationship to IP, or if unrelated, the cause.

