3.4 Safety Objectives

Safety objectives will be to assess treatment-emergent adverse events (TEAEs) after each PSMA PET scan.

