5.4 Safety Evaluations

- Incidence of TEAEs after each PSMA PET scan.

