13.3 Lost to Follow-up

A patient will be considered lost to follow-up if they fail to return for the second PET scan (flotufolastat (^{18}F)) within 10 calendar days of the first PET scan (piflufolastat (^{18}F)) and is unable to be contacted by the study site staff.

The following actions must be taken if a patient fails to return to the clinic for a required study visit:

- The site will attempt to contact the patient and reschedule the missed visit (no later than within 10 calendar days of the first PET scan) and counsel the patient on the importance of maintaining the assigned visit schedule and ascertain if the patient wishes to and/or should continue in the study;
- Before a patient is deemed lost to follow-up, the investigator or designee will make every effort to regain contact with the patient (where possible, three attempts to contact). These contact attempts should be documented in the patient's medical record or study file;
- Should the patient continue to be unreachable, they will be considered to have withdrawn from the study with a primary reason of lost to follow-up.

14 **PROTOCOL VIOLATIONS**

A protocol violation occurs when the patient, investigator, or sponsor fails to adhere to significant protocol requirements affecting the inclusion, exclusion, patient safety, and primary endpoint criteria. Protocol violations for this study include, but are not limited to, the following:

- Failure to meet inclusion/exclusion criteria (see [Sections 6.2](#) and [6.3](#));
- Use of a prohibited concomitant medication (see [Section 7.2](#));
- Radiopharmaceutical administration but no subsequent PET scan;
- Use of a non-approved PET/CT scanner.

Significant non-compliance with Good Clinical Practice (GCP) guidelines will also result in a protocol violation. The sponsor will determine if a protocol violation will result in the withdrawal of a patient.

When a protocol violation occurs, it will be discussed with the investigator and a protocol violation form detailing the violation will be generated. This form will be signed by a sponsor representative and the investigator. A copy of the form will be filed in the investigator site's file and in the sponsor's files.

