### 7.2. Adverse Events

A TEAE is defined as an AE that started or worsened after administration of piflufolastat up to the final safety monitoring telephone call after the administration of flotufolastat (18F) (Visit 4). All AE verbatim terms will be coded by system organ class (SOC) and preferred term (PT) using Medical Dictionary for Regulatory Activities (MedDRA) version 26.1 or higher. TEAEs will be summarized overall and categorized by those attributable to piflufolastat and those attributable to flotufolastat, as described in

[Table 3](#).

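### TEAEs are probed for after flotufolastat but not solicited after piflufolastat, so the two by-tracer safety percentages are not like for like

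*Protocol*

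**What the plan says.** Protocol 3.4 covers both tracers: "Safety objectives will be to assess treatment-emergent adverse events (TEAEs) after each PSMA PET scan". The endpoint in Protocol 5.4 is "Incidence of TEAEs after each PSMA PET scan".

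Protocol 12.1 sets two ways of finding events.

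- **Flotufolastat:** the investigator "will probe, via discussion with the patient at the post-procedural safety monitoring telephone call 24 hours after the" flotufolastat scan.
- **Piflufolastat:** no post-piflufolastat PET "safety monitoring telephone call is planned and AEs will not be solicited, but any AEs volunteered by the patient will be reported". Collection takes place when the patient comes back for Scan 2. The reason given is that the patient would have the first scan whether or not he joined the study.

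Protocol 10.3, step 1, tells the site at Visit 3 (Days 2 to 10) to record AEs since Visit 2. This step comes before the flotufolastat injection. It does not say whether the patient is to be asked.

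Protocol 15.5 plans TEAE summaries, with number and percentage of patients, for both tracers. SAP 7.2 does the same: "TEAEs will be summarized overall and categorized by those attributable to piflufolastat and those attributable to flotufolastat". SAP Table 3 ends each attribution window at about one day after dosing. The SAP text has no caveat about the difference in ascertainment.

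**The concern.** One statistic, the percentage of patients with a TEAE, is to be reported for two tracers using two methods of finding events. Direct questioning at 24 hours can be expected to bring out minor events that a patient would not raise unprompted up to several days later. The two percentages could therefore differ even if the tracers were equally well tolerated, and a reader of the table could not separate tolerability from method.

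What is at stake is the meaning of a stated endpoint for Scan 1 and the reading of a descriptive table. The primary SUV analysis and the detection rates do not depend on it.

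**Working it through.** The documents state no expected TEAE rate, capture rate or safety power, so there is no plan figure to reproduce. The check compares the sections and then adds a labelled illustration.

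**1. How events are found.** After flotufolastat they are probed for by telephone at 24 hours (Protocol 12.1). After piflufolastat they are not solicited (Protocol 12.1), but are recorded at Visit 3 (Protocol 10.3, step 1). Sites could read these two sections differently: one might ask at Visit 3 while another only writes down what is offered.

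**2. Time at risk.** In Protocol Table 2 the piflufolastat window runs to flotufolastat dosing. With Scan 2 as late as Day 10, that is up to 10 − 1 = 9 days, against about 1 day for flotufolastat. This would push piflufolastat counts up. SAP Table 3 caps both windows at about one day, which removes most of that effect. It roughly aligns time at risk and leaves the method of finding events unequal.

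**3. Recall gap under the SAP windows.** The piflufolastat window closes at about Day 2 and Visit 3 falls on Days 2 to 10, so collection comes 2 − 2 = 0 to 10 − 2 = 8 days after the window closes. For flotufolastat, the call falls at about the end of the window.

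**4. Illustration only.** Assume equal true risk p for both tracers, full capture after flotufolastat, and capture c after piflufolastat. N = 52 is the planned minimum of evaluable patients (Protocol 15.1); p and c are assumptions.

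- Expected patients with an event: N × p (flotufolastat) and N × p × c (piflufolastat).
- Chance of seeing none: (1 − p)^N and (1 − p × c)^N.

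| p | Flotufolastat expected | Piflufolastat expected, c = 75% / 50% / 25% |
|---|---|---|
| 2% | 1.04 | 0.78 / 0.52 / 0.26 |
| 5% | 2.6 | 1.95 / 1.3 / 0.65 |
| 10% | 5.2 | 3.9 / 2.6 / 1.3 |

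At p = 5%, the chance of no piflufolastat event is 14%, 27% or 52% for the three capture rates, against 7% for flotufolastat. The apparent ratio is 1/c, that is 1.3, 2 or 4, whatever p is. It restates the assumed capture rate and is not evidence of the actual size.

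**5. A low-end anchor from the documents.** Protocol 2.1.2 lists adverse reactions in 5, 4 and 3 of 747 patients. (5 + 4 + 3)/747 = 12/747 = 1.6%, or 52 × 0.016 = about 0.8 expected in this study. These are listed reactions, not all TEAEs, so the TEAE rate may be higher. At this level the gap between columns would be less than one patient.

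**The case against.** The strongest reply is that the asymmetry is deliberate and disclosed. Piflufolastat is routine care, flotufolastat is the only investigational product, and piflufolastat events receive no causality assessment by design. The safety objective is to assess, whereas the primary objective is to compare. Protocol 15.5 describes the safety summary as descriptive and for the investigational product. Visit 3 already includes an AE recording step. The TFL specifications are in a separate document (SAP 1), so table titles and footnotes cannot be seen.

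Much of this stands. No formal comparison is planned, and piflufolastat events are not left uncollected. The routine-care reason explains why there is no telephone call. It does not explain percentages by tracer without a caveat in the SAP: the endpoint names each scan, and Protocol 15.5 goes on to summarise both tracers. A Visit 3 recording step does not equal probing when Protocol 12.1 says that events are not solicited. Labels may exist in the TFL specifications, but the SAP does not call for them.

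A reader might also infer that the design would conceal a safety problem with piflufolastat. The documents do not support that. SAEs after either tracer must be reported within 24 hours of the investigator becoming aware (Protocol 12.4.1), and suspected piflufolastat reactions go to the marketing authorization holder or the FDA. The gap is mainly in non-serious events that patients do not mention.

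**Conclusion.** The point holds as a fault of comparability in a descriptive safety table. The piflufolastat percentage is expected to be low relative to the flotufolastat percentage, on the assumption that unsolicited collection finds fewer events than direct questioning. That is a direction only; its size cannot be computed from the documents. The protocol's two statements on Visit 3 collection also need to be reconciled.

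A reader might infer that the bias is greatest in patients who leave after Scan 1. Such patients stay in the safety set without reaching Visit 3, but the documents do not establish that claim. Protocol 13.1 has the reason for withdrawal recorded if known, Protocol 13.3 requires contact attempts, and SAP 2.3.2 regards this withdrawal as unlikely. Nor would a higher flotufolastat percentage in the final table show that it is the less well tolerated tracer.

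**What to change.** **If collection can still be changed.** Amend Protocol 12.1 and 10.3, step 1, to agree: at Visit 3, before the flotufolastat injection, the site asks the same AE question as at Visit 4, referring to the period since Scan 1. For patients who do not return, ask it during the contact that Protocol 13.3 already requires ("The site will attempt to contact the patient and reschedule the missed visit"). If the change comes part-way through, the piflufolastat column will mix two methods and still needs a note.

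**If collection is complete or stays unsolicited.** State in SAP 7.2 that piflufolastat TEAEs are volunteered and flotufolastat TEAEs solicited, label the tables accordingly, and draw no between-tracer conclusion on incidence. The final SAP is to be signed before database lock.

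**Cost.** The first route takes a short protocol amendment and one scripted question at existing contacts, with slightly more piflufolastat AEs to record; causality still need not be assigned. The second takes one sentence and table titles. The remaining recall gap of up to about 8 days would not be removed by asking at Visit 3, and the report should mention it.

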12.2 Adverse Event Severity

The National Cancer Institute’s Common Terminology Criteria for Adverse Events (CTCAE) Version 5 (November 27, 2017) will be used to assess and grade event severity, including, if applicable, laboratory abnormalities judged to be clinically significant. The severity grading is provided below (Table 3).

Table 3: CTCAE (V5) AE Severity Grading

Severity (Toxicity Grade)	Description
Grade 1	Mild; asymptomatic or mild symptoms; clinical or diagnostic observations only; intervention not indicated.
Grade 2	Moderate; minimal, local, or non-invasive intervention indicated; limiting age-appropriate instrumental ADL.*
Grade 3	Severe or medically significant but not immediately life-threatening; hospitalization or prolongation of hospitalization indicated; disabling; limiting self-care ADL**.
Grade 4	Life-threatening consequences; urgent intervention indicated.
Grade 5	Death related to AE.

Abbreviations: ADL=activities of daily living; AE=adverse event; CTCAE=Common Terminology Criteria for Adverse Events.

*Instrumental ADL refers to preparing meals, shopping for groceries or clothes, using the telephone, managing money, etc.

** Self-care ADL refers to bathing, dressing and undressing, feeding self, using the toilet, taking medications, and not bedridden.

If the experience is not covered in the modified criteria, the guidelines shown in Table 4 below will be used to grade severity. It should be pointed out that the term “severe” is a measure of intensity and that a severe event is not necessarily serious.

Table 4: AE Severity Grading

Severity (Toxicity Grade)	Description
Mild (1)	Transient or mild discomfort; no limitation in activity; no medical intervention or therapy required. The patient may be aware of the sign or symptom but tolerates it reasonably well.
Moderate (2)	Mild to moderate limitation in activity, no or minimal medical intervention/therapy required.
Severe (3)	Marked limitation in activity, medical intervention/therapy required, hospitalizations possible.
Life-threatening (4)	The patient is at risk of death due to the adverse experience as it occurred. This does not refer to an experience that hypothetically might have caused death if it were more severe.
Death (5)	Death related to AE.

Abbreviations: AE=adverse event.

